Cover Page for ClinicalTrials.gov

Document:

Protocol and Statistical Analysis Plan

Official Study Title:

Mi Puente: My Bridge to Better Cardiometabolic Health and Well-Being

NCT#

NCT02723019

Document Date

January 24, 2017

Mi Puente Protocol

The proposed randomized controlled trial will enroll 560 individuals according to the inclusion and exclusion criteria that follow and randomly assign them to a study group in order to test the effectiveness of Mi Puente, a nurse and volunteer peer team intervention (n=280) versus Usual Care, a best practices comparison (n=280) in Hispanics with multiple chronic physical and behavioral conditions.

Inclusion criteria:

1. Hispanic ethnicity (any race)
2. Is currently inpatient at Scripps Mercy Hospital Chula Vista
3. Age 18 years and older
4. Two or more cardiometabolic conditions (e.g., obesity, diabetes, hypertension, ischemic heart disease, congestive heart failure, other chronic coronary conditions, dyslipidemia)
5. One or more behavioral health concern(s) (e.g., broadly defined and related to mental health, medication adherence, life stressors, healthcare use, substance use)
6. Access to telephone (mobile or landline)

Exclusion criteria:

1. Pregnancy
2. Serious life-threatening condition with life expectancy <6 months.
3. Psychiatric morbidity or neurological/cognitive impairment of sufficient severity to preclude participation in the intervention.
4. Plans to discharge to location other than home (e.g., inpatient rehabilitation or nursing care)
5. Does not speak Spanish or English

Patients who are potentially eligible (based on demographics, diagnoses) will be identified through a daily review of electronic medical records (EMR) and asked by their bedside nurse if they are willing to discuss the study with research staff. Those who agree will be approached by a trained bilingual research assistant, who will obtain verbal informed consent and administer an evidence-based behavioral health screener. Patients with one or more behavioral health needs identified either via screening or EMR review (e.g. documented, pre-existing mental health diagnosis) will be deemed eligible, provided with a detailed description of the study and if interested will be asked to provide written informed consent.

Behavioral Health Screener will comprise of the following parameters:

1. Emotional Well-being, measured by the PROMIS Anxiety and Depression forms,
2. Smoking, measured by number of cigarettes smoked per day
3. Alcohol consumptions (AUDIT-C)
4. Stress, measured by means of the Perceived Stress Scale, 4-item
5. Medication Adherence, measured by how many days/weeks the recommended medications are taken, reported by the patient
6. Healthcare access, patients' report on where they normally seek medical care.

After informed consent is obtained, assignment will be unveiled to the participant by the consenting research assistant and the participant will be assigned also with an ID number which will be used in all

procedures using de-identified data.

Participants assigned to the Usual Care (UC) group will be treated using best practice evidence-based discharge procedures, involving a team-based approach to enhance coordination of care for individuals at high risk for readmission.

Participants assigned to the Mi Puente group will be receiving usual care along with the Mi Puente discharge procedure. The latter involves individualized support from a Behavioral Health Nurse while inpatient, a follow-up call from the Behavioral Health Nurse during post-discharge week 1 and weekly supportive phone calls from a Volunteer Peer Mentor during post-discharge weeks 1-4. The intervention will focus on building resources, skills, knowledge and on empowering patients and connecting them with appropriate outpatient services.

EMR of all study subjects will be audited for specific information relevant to the trial (e.g. diagnoses, medication, complications, readmissions, length of stay) at baseline and for readmissions at 30-days and 180-days after baseline.

All study subjects will participate in three assessments of approximately 30-60 minutes duration at baseline and at 3 months and 6 months after baseline. Baseline assessment will be performed prior to hospital discharge in person and the month-3 and month-6 assessments will be conducted by telephone.

Data collected during these assessments will involve the following patient-reported indicators:

1. Demographic information (study-specific/standard item)
2. Physical symptoms, measured via the PHQ-15
3. Quality of life, measured by the PROMIS General Health Scale
4. Healthcare access and barriers, measure adapted from the HCHS/SOL
5. Patient activation, measured by the Patient Activation Measure
6. Support resources for disease management, measured by means of the Chronic Illness Resources Survey.

Guided by the RE-AIM framework, the program evaluation will examine the success of Mi Puente versus Usual Care in 1) Reaching a representative segment of the population (Reach); 2) Achieving meaningful outcomes through a well-implemented intervention (Efficacy/Implementation); and 3) Creating an intervention that can be adopted by and maintained in a real-world environment (Adoption/Maintenance). As part of the evaluation, 20 participants will be invited to attend focus groups to share their experiences with the intervention (2-3 groups). The Behavioral Health Nurse and Volunteer Peer Mentors will also serve as “participants” via their involvement in evaluating the treatment fidelity of and their experiences with Mi Puente.

Cost-effectiveness Analysis (CEA) of the Mi Puente intervention relative to Usual Care only will be conducted focusing on services delivered by the two care partners (Scripps/San Ysidro Health center) and Mi Puente coordination over the 6-month study period. Cost-effectiveness will be estimated using the Incremental Cost Effectiveness Ratio (ICER). The estimated ICER will be compared to CEA standards

and similar interventions to provide context for the cost-effectiveness of Mi Puente.

Timeline: The study will be conducted over 5 years, 07/01/15 – 06/30/20. The first 6 months will be devoted to start-up. Eligible patients will be enrolled between months 7 and 46 and the recruitment target is approximately 28 patients per month during this period, with post-discharge telephone intervention for Mi Puente group participants concluding in month 47. Follow-up telephone assessments of patient-reported outcomes will be completed between months 10 and 52. Focus groups will follow in months 53-54 and the last 6 months will be devoted to statistical analyses and report preparation.

Study participants will be offered gift cards as an incentive to complete all assessments. Study participants will receive compensation after baseline (\$20), month-3 (\$20) and month-6 (\$25) assessments in the form of gift cards. The total incentive for participants who will complete all assessments will be \$65. Gift cards will be given after completion of each assessment; that is at baseline, 3-months and 6 months.

Patients interested in the study will be approached by a trained bilingual staff member while inpatient. The bilingual staff member will introduce the study to the participant and obtain verbal consent to administer evidence-based behavioral health screening. Patients who are deemed eligible to participate in the study will be provided with a copy of the consent form and will review all content together with the staff member both in Spanish and English. Adequate opportunity will be provided to the potential participant to consider all options and ask questions; care will be taken to ensure that all participants understand the information and that their participation is voluntary. Prior to each follow-up appointment, research staff will remind participants of the procedures and the voluntary nature of their participation.

Statistical Analysis Plan

Sample size

Power and Sample Size

The target study sample size is 560 participants allocated equally to the two groups ($n = 280/\text{group}$). Sample size estimates were calculated based on the primary outcome of hospital utilization at 30 and 180 days, and the secondary outcome of changes in patient-reported outcomes. All estimates were generated using RMASS2 assuming a statistical significance level of .05 (two-tailed), and targeting at least 80% power. Sample size estimates were adjusted to up to 20% total attrition. Power analyses indicated that a sample size of 558 is needed at baseline to find a statistically significant incidence rate ratio of expected magnitude with 80% power. For patient-reported outcomes, we estimated an effect size of $d = 0.50$ as a clinically significant change. Using parameters defined above, 280 participants are needed to find a statistically significant difference between groups.

Analytic Plan

All analytic strategies will follow intent-to-treat principles. Preliminary data screening and cleaning will be conducted, and statistical testing and effect size consultation will be used to determine if random assignment has resulted in statistical equivalence between groups. Significant covariates will be added to adjust for nonequivalence. Analyses of hospital utilization (primary outcome) and patient-reported

outcomes will be conducted using multi-level modeling and the appropriate link function for a target outcome. Analyses will include “group” (Mi Puente or Usual) as the between-subjects factor, “time” (assessment dates) as the within-subjects factor, and a cross-level, “group-by-time” interaction effect. Analyses will be conducted in IBM SPSS Statistics 22.0 (IBM, Inc., Armonk, NY, UK) and MPLUS (Muthen & Muthen, Los Angeles, CA, USA). Effect size indicators and confidence intervals will also be examined and reported.

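### The protocol does not require the baseline interview to precede unveiling of assignment or study nurse contact, so secondary patient-reported baselines can be taken after participants know their arm

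*Combined protocol and SAP*

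**What the plan says.** The Mi Puente Protocol describes three events within one hospital stay.

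- Unveiling: "After informed consent is obtained, assignment will be unveiled to the participant by the consenting research assistant".
- Interview: "Baseline assessment will be performed prior to hospital discharge in person". Months 3 and 6 follow by telephone.
- Study nurse contact, Mi Puente arm only: "individualized support from a Behavioral Health Nurse while inpatient".

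On content, the protocol states: "Data collected during these assessments will involve the following patient-reported indicators". The list comprises demographics, PHQ-15, PROMIS General Health, access and barriers to care, the Patient Activation Measure and the Chronic Illness Resources Survey.

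Power and Sample Size in the Statistical Analysis Plan names "the secondary outcome of changes in patient-reported outcomes" and plans for d = 0.50 "as a clinically significant change". The Analytic Plan uses a multilevel model with group, time and their interaction. It also says: "Significant covariates will be added to adjust for nonequivalence".

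**The concern.** Consent is the only stated condition for unveiling, and discharge is the only stated limit for the interview. Staff who follow the text can tell a participant the arm, and even begin nurse support, before the interview takes place. The baseline would then be measured after assignment had begun to act.

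That matters because the secondary outcomes are changes, so the baseline enters the estimate directly. There are two routes, and they differ.

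- **Nurse contact.** The intervention aims to strengthen resources, skills, knowledge and empowerment, which overlap with the activation and support-resource scales. Early contact would plausibly raise the Mi Puente baseline, and the effect would be understated.
- **Knowledge of the arm alone.** Self-report could move either way, and the documents support no direction.

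The pre-consent screener does not solve this. It covers anxiety and depression, smoking, alcohol, stress, medication adherence and usual place of care, and contains none of the interview instruments listed above.

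**Working it through.** The plan gives no figure on this point, so there is none to reproduce. The check is a comparison of the stated timings, followed by an illustration on assumed values.

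**1. Stated timings**

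| Step | Timing given | Ordered against the interview? |
|---|---|---|
| Behavioral health screener | After verbal consent, before written consent | Different instruments |
| Unveiling | After informed consent | No |
| Study nurse support | During the stay | No |
| Baseline interview | In person, before discharge | – |

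The timeline, gift-card and consent paragraphs do not settle the order. Two sequences satisfy every sentence:

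- consent, interview, unveiling, nurse, discharge;
- consent, unveiling, nurse, interview, discharge.

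**2. How a shift enters the estimate**

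Let δ be the true follow-up difference in score SDs and s the between-arm baseline shift caused by assignment (positive = benefit in Mi Puente). Let q be the fraction of interviews held after unveiling, equal in both arms, p the share of a reporting shift still present at follow-up, and r the baseline-to-follow-up correlation.

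- Baseline difference = q·s
- Follow-up difference = δ + p·q·s
- Change contrast = δ − (1 − p)·q·s
- Level-only contrast = δ + p·q·s
- Baseline-adjusted contrast with p = 0: δ − r·q·s

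A transient shift (p = 0) is subtracted in full from the change contrast. A reporting shift that persists equally (p = 1) cancels there but stays in the level-only comparison. A real early gain from nurse contact is part of the treatment effect, so any of it that lasts belongs in δ and p = 0 applies.

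With equally spaced visits at 0, 3 and 6 months, a linear group-by-time slope is (−3·y0 + 3·y6)/18 = (y6 − y0)/6. The 6-month contrast is y6 − y0, and the baseline shift carries weight −1.

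**3. Illustration**

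From the plan: 560 participants, up to 20% attrition, two-sided .05, d = 0.50. Assumed: r = 0.5, q = 1, p = 0, and the values of s.

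- Per arm: 560 × 0.80 / 2 = 224
- SD of change: √(2(1 − 0.5)) = 1 score SD, so d = 0.50 has the same meaning on either scale
- Standard error: 1 × √(2/224) = 0.0945
- Power ≈ Φ(estimate/0.0945 − 1.96)

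| s (SD) | Estimate | Estimate/SE | Power |
|---|---|---|---|
| 0 | 0.50 | 5.29 | >99% |
| 0.1 | 0.40 | 4.23 | 98.8% |
| 0.2 | 0.30 | 3.17 | 88.8% |
| 0.3 | 0.20 | 2.12 | 56.2% |

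For r from 0.3 to 0.7, power at s = 0.2 runs from 76.5% to 98.4%. Bias scales with q: at q = 0.5, s = 0.2 costs 0.10, as in the 0.1 row. With the opposite sign, s = −0.1 gives 0.60. Baseline adjustment at r = 0.5 and s = 0.1 leaves 0.50 − 0.05 = 0.45, so only part of the bias is removed.

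If δ = 0, a transient shift of 0.1 SD of either sign raises two-sided rejection from 5% to about 18.5% at r = 0.5. That figure depends on the shift having gone by follow-up.

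**4. Level-only comparison**

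Its standard error is √(2/224) = 0.0945 whatever r is. Relative to change, the ratio is 1/√(2(1 − r)): 1.00 at r = 0.5 and 1.29 at r = 0.7. Power at 0.50 SD is above 99%. For s = 0.1 and δ = 0.50, it gives 0.50 if the shift is transient and 0.60 if it persists fully.

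**The case against.** The strongest reply is that this is an omission. Unveiling after consent need not mean immediately after, calling the assessment baseline suggests that it comes first, and the harmless sequence satisfies every sentence. The consent form, which is not among the documents reviewed, might state the order. This stands as a limit on the claim: a reader might infer that the baselines are taken after unveiling, and the documents do not say so. It does not remove the gap, because the text also allows the harmful sequence.

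The size of the shift is also pure assumption, and a persistent reporting shift would cancel in the change analysis while biasing the level-only one. Both points are correct, and the results above are conditional for that reason.

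A reader might also infer that the primary outcome is compromised. The documents do not support that: hospital utilization comes from medical-record audit. The only route is indirect, if interview scores shifted by assignment were treated as chance imbalance and added as covariates. The Analytic Plan does not name them for that use.

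Finally, no passage lists which instruments are the secondary outcomes. That they are the interview scales is a reasonable presumption.

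**Conclusion.** The gap is real and should be closed. As written, the protocol permits secondary patient-reported baselines to be collected after participants know their arm or after nurse contact has begun. It does not state that this happens.

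Neither the size nor a single direction can be taken from the documents. Under the assumed transient shifts of 0.1 to 0.3 SD towards benefit in all interviews, the planned 0.50 SD difference loses 20% to 60% of its estimated size. At r = 0.5 power remains high for the smaller shifts and falls to 56% at 0.3 SD. Smaller shifts, or fewer affected interviews, give proportionally less bias. Understatement is the more plausible result for early nurse contact; for knowledge of the arm alone the sign is open. The primary outcome is not directly affected, so this ranks below a threat to the main conclusion. It still merits action, because analysis cannot fully recover a baseline taken too late.

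**What to change.** In the assignment paragraph of the protocol, make unveiling conditional on both written consent and a completed baseline interview, and place study nurse contact after unveiling. In addition:

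- record the date and time of consent, interview, unveiling and first study nurse contact;
- report by arm how many interviews followed unveiling;
- do not use interview scores taken after unveiling as covariates for the primary outcome;
- add a sensitivity analysis comparing month-3 and month-6 levels between the randomized arms without baseline, stating that it removes a baseline-only shift but not a persistent reporting shift.

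If the interview already comes first in practice, the sequence needs one sentence and the time stamps confirm it. Otherwise, unveiling and the start of study nurse contact wait for an interview of 30 to 60 minutes. Some short-stay patients may leave before assignment. They would be lost before assignment (provided that assignment is also drawn at that point) and should be counted under Reach. The documents give no basis for estimating their number. The level-only analysis is less precise than change when r exceeds 0.5.

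New wording helps only later participants. With month 1 as July 2015, month 7 is January 2016 and the January 2017 document date falls in month 19, so about 12 of the 40 planned enrolment months had passed. The number already enrolled is not given, and for those participants the counts and the sensitivity analysis are the available safeguards.

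### Possible clustering by peer mentor in the Mi Puente arm is not addressed in the model or the sample size; if mentors are shared and differ in effect, standard errors are understated

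*Combined protocol and SAP*

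**What the plan says.** **Delivery.** In the Mi Puente Protocol, participants are randomised individually. Both arms receive usual care. The Mi Puente arm adds support and one call from a Behavioral Health Nurse, and "weekly supportive phone calls from a Volunteer Peer Mentor during post-discharge weeks 1-4". The program evaluation text shows that there is more than one mentor: "The Behavioral Health Nurse and Volunteer Peer Mentors will also serve as" participants in the evaluation. The documents give no number of mentors or caseload, and do not say whether one mentor makes all the calls to a given participant.

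**Analysis.** The Analytic Plan says that analyses of hospital utilization and patient-reported "outcomes will be conducted using multi-level modeling and the appropriate link function for a target outcome". It then names group as the between-subjects factor, time as the within-subjects factor, and a cross-level interaction of the two. The levels named are therefore time and person. No mentor or nurse level, random effect for provider, or cluster-robust standard error is mentioned.

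**Sample size.** Under Power and Sample Size: "The target study sample size is 560 participants allocated equally to the two groups". The calculation uses a two-sided .05 level, "targeting at least 80% power", and concludes that "a sample size of 558 is needed at baseline to find a statistically significant incidence rate ratio of expected magnitude". The one adjustment given is for loss to follow-up: "Sample size estimates were adjusted to up to 20% total attrition". No ICC or design effect appears.

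**The concern.** Individual randomisation makes participants independent at entry, but treatment delivery can create correlation afterwards. If one mentor supports several participants and mentors differ in how much they help, outcomes within a mentor's caseload move together. This happens in one arm only, so the trial is partially nested. A model with time within person and nothing above it treats the 280 Mi Puente participants as 280 independent pieces of information.

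Shared caseloads are an inference, but a reasonable one. Avoiding any sharing would take 280 volunteers, and enrolment runs from month 7 to month 46, which gives ample time for a mentor to take on participants in succession. Differences between mentors are also plausible, because the intervention is personal support aimed at skills, knowledge and empowerment.

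At stake are the confidence intervals that the plan undertakes to report, the error rate of the group comparisons, and the power for the primary outcome, where the target of 560 exceeds the stated need of 558 by only two participants.

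**Working it through.** **1. The plan's own figure.** The 558 cannot be reproduced, because the incidence rate ratio, event rates and dispersion are not given. What can be derived: 558 × 0.8 = 446, or 223 per arm after attrition. The margin in the target is 560/558 = 1.0036, so a variance inflation of about 0.4% uses it up.

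**2. Inputs.**
- From the documents: 280 per arm, two-sided .05, 80% power, up to 20% attrition.
- Assumed, because the documents do not give them: 10, 20 or 40 mentors with equal caseloads (m = 28, 14 or 7), one mentor per participant, and a mentor ICC of 0 to .05.

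**3. Formulas** (continuous scale, clustering in one arm, equal total variances).
- Design effect in the Mi Puente arm: DE = 1 + (m − 1) × ICC.
- Variance ratio for the group difference: VR = (DE + 1)/2.
- True two-sided error when mentor is ignored: 2 × [1 − Φ(1.96/√VR)].
- Power of a correctly sized test that had 80% at VR = 1: Φ(2.80/√VR − 1.96).

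**4. Two cells worked through.**
- 40 mentors, ICC .01: DE = 1 + 6 × .01 = 1.06; VR = 1.03; √VR = 1.015; error 5.3%; power 79%.
- 10 mentors, ICC .05: DE = 1 + 27 × .05 = 2.35; VR = 1.675; √VR = 1.294; error 13.0%; power 58%.

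**5. Full grid** (formula values).

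| Mentors (caseload) | Result | ICC 0 | ICC .01 | ICC .02 | ICC .05 |
|---|---|---|---|---|---|
| 10 (28) | true error | .050 | .066 | .082 | .130 |
| | power | 80% | 75% | 70% | 58% |
| 20 (14) | true error | .050 | .058 | .065 | .089 |
| | power | 80% | 77% | 75% | 68% |
| 40 (7) | true error | .050 | .053 | .057 | .068 |
| | power | 80% | 79% | 78% | 74% |

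Simulation of the unadjusted test (20,000 runs per cell, zero average effect, mentors varying around it) agrees at ICC .01, .02 and .05: .065, .084 and .129 for 10 mentors; .054, .065 and .090 for 20; .054, .057 and .070 for 40.

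**6. Effect of attrition.** With 224 left in the arm and the same mentors, caseloads shrink. The worst cell becomes m = 22.4, DE = 2.07, VR = 1.535, error 11.4%.

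**7. Patient-reported outcomes at d = 0.50.** In a simple two-group calculation with 224 per arm, the standardised effect is 0.5 × √(224/2) = 5.29, and power is above 99%. At VR = 1.535 it is Φ(5.29/1.239 − 1.96), still about 99%. The plan's own requirement of 280 participants is not said to be a total or per group, and its longitudinal inputs are not given, so this only indicates that the margin may be large.

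**Limits.** The primary outcome is a count analysed as a rate ratio, so steps 3 to 6 are only a guide there. The power formula uses normal quantiles; with as few as 10 mentors, small-sample degrees of freedom would lower power somewhat further.

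**The case against.** A reader might infer that the trial's error rate does exceed .05. The documents do not support that.
- Shared mentors are inferred, not stated.
- The number of mentors and the ICC are unknown. At ICC 0 the error rate is .05 for any number of mentors.
- Because participants are randomised individually, the strict null of no effect in any participant implies no mentor effect, and the test keeps its level. Inflation needs mentors who differ in effect while averaging to zero.
- With 20 to 40 mentors and an ICC of .01, the excess is under one percentage point.

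A reader might also infer that 80% power is lost for every outcome. That is not supported either. For patient-reported outcomes the text does not say whether 280 is a total. If it is, the target of 560 leaves a large margin, and the simple calculation above agrees.

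Three further points carry weight. The plan omits a mentor level but does not exclude one, and multilevel modelling is already intended. If mentors rotate across the four weekly calls, nesting each participant in a single mentor is only an approximation. Treating each Usual Care participant as their own cluster is also an assumption, because usual care is itself team-based, although both arms receive it.

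What remains is that the model terms are listed, mentor is not among them, and an analyst who followed the text would treat the arm as unclustered. The intervals do not depend on the null: they are too narrow whenever shared mentors differ in effect, whatever the average effect.

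**Conclusion.** The concern holds in conditional form. The plan has a one-arm delivery structure that probably produces shared mentors, and neither the model nor the sample size addresses it. If caseloads are shared and the mentor ICC is positive, the standard errors and intervals for the group effects are too small; if the ICC is 0, nothing is wrong.

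Under the assumed 10 to 40 mentors and ICC of .01 to .05, the true standard error is about 1.01 to 1.29 times the reported one. The true error of a nominal 5% test is then about 5.3% to 13%, and the primary outcome's power falls from a nominal 80% to about 79% to 58% once clustering is modelled. The low end is negligible and the high end is material; the documents do not show where the trial lies. That uncertainty is a reason to collect the identifier and pre-specify the analysis, not to assert that the results will be invalid.

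**What to change.** 1. Record a mentor ID for each Mi Puente participant, or the main mentor if calls rotate. This may be hard to recover later.
2. In the Analytic Plan, pre-specify a partially nested analysis for the primary and patient-reported outcomes, at minimum as a sensitivity analysis: a mentor random effect in the Mi Puente arm only, each Usual Care participant as their own cluster, and a small-sample correction where the software offers one. Confirm beforehand that the chosen package can do this for the count outcome.
3. Report the number of mentors, the caseloads and the estimated mentor ICC.
4. Under Power and Sample Size, state that the 558 and the 80% power assume no mentor clustering.

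The cost is one variable and a few sentences of SAP text. Intervals will be somewhat wider, and with few mentors the mentor variance will be estimated imprecisely. One limit remains: if there is a single Behavioral Health Nurse, as the singular wording suggests, no model can separate that nurse's effect from the arm effect, and the report should say so.

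### The 30- and 180-day record audits cover readmissions only, and nothing planned captures death, so fewer readmissions could not be checked against more deaths

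*Combined protocol and SAP*

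**What the plan says.** The Mi Puente Protocol section provides for an electronic record audit of every subject. The baseline audit is broad and its list is given by example. The follow-up part is narrow; the sentence ends "complications, readmissions, length of stay) at baseline and for readmissions at 30-days and 180-days after baseline". The telephone assessments at months 3 and 6 collect six patient-reported indicators, and vital status is not among them.

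The exclusion criteria rule out "Serious life-threatening condition with life expectancy <6 months", a horizon about as long as the 180-day window. Qualifying conditions include ischemic heart disease and congestive heart failure, and also obesity, hypertension, diabetes and dyslipidemia.

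The SAP (Power and Sample Size) names the "primary outcome of hospital utilization at 30 and 180 days" and expresses its effect as an incidence rate ratio. It allows for up to 20% attrition without saying whether deaths are included. The Analytic Plan adopts intent-to-treat and a multi-level model: "Analyses will include “group” (Mi Puente or Usual) as the between-subjects factor, “time” (assessment dates) as the within-subjects factor", plus their interaction. It gives no rule for deaths, time at risk or censoring, and no mortality summary.

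**The concern.** Death ends the chance of readmission. In a readmission trial among inpatients with several chronic conditions, the reader needs to know who died, when, and in which arm. Without a planned death field, the analyst cannot reliably censor at death, form a composite endpoint or tabulate mortality by arm.

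Take a participant who dies at home on day 10 without having been readmitted. A readmissions-only audit finds nothing. Intent-to-treat keeps that participant in the analysis, and no stated rule makes the record anything other than zero events. In the patient-reported data the same participant would look like a missed assessment. Two things are at stake: some distortion of the primary rate ratio, and the absence of any planned mortality comparison to read beside it.

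**Working it through.** **The plan's own figure.** The SAP says that "a sample size of 558 is needed at baseline to find a statistically significant incidence rate ratio of expected magnitude with 80% power". This cannot be reproduced, because the base rate, rate ratio, dispersion and within-person correlation are not given. As a yardstick I solved backwards from 558 × 0.8 / 2 = 223 evaluable per arm, using a Poisson Wald test on the log rate ratio with two-sided 0.05 and 80% power:

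n per arm = (1.96 + 0.842)² × (1/μ₀ + 1/μ₁) / (ln IRR)²

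The detectable IRR is about 0.48 at μ₀ = 0.2 admissions per person, 0.66 at 0.5, 0.68 at 0.6 and 0.75 at 1.0 (assumed rates, no overdispersion).

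**Assumptions for the distortion.** The documents give no mortality or readmission rate. I assume 0.6 readmissions per person per 180 days, deaths spread evenly over the window, no treatment effect on readmission, and decedents readmitted at k times the survivors' rate while alive. For mortality d:

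- Mean readmissions per randomised person: M(d) = 0.6 × [(1 − d) + k·d/2]
- Mean fraction of the window alive: E(d) = 1 − d/2
- IRR without time at risk = M(high) / M(low)
- IRR per day alive = [M(high)/E(high)] / [M(low)/E(low)]

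The ratios are for the higher-mortality arm over the lower, and the 0.6 cancels.

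For 5% versus 10%:

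- k = 1, no time at risk: 0.95 / 0.975 = 0.974. Per day alive: 1.00.
- k = 3, no time at risk: 0.630 / 0.615 = 1.024. Per day alive: (0.630/0.95) / (0.615/0.975) = 1.051.

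| Mortality | k = 1, no time at risk | k = 3, no time at risk | k = 3, per day alive |
|---|---|---|---|
| 3% vs 6% | 0.970/0.985 = 0.985 | 1.030/1.015 = 1.015 | 1.030 |
| 5% vs 10% | 0.974 | 1.024 | 1.051 |
| 5% vs 15% | 0.925/0.975 = 0.949 | 1.075/1.025 = 1.049 | 1.105 |

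At k = 2, M(d) = 0.6 whatever d is, so the ratio without time at risk is exactly 1. Below k = 2 the higher-mortality arm looks better; above it, worse. With equal mortality and the same k in both arms, the ratio is 1.00.

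**Binary check.** Let p be the 180-day readmission risk in the absence of death. With constant hazards λ = −ln(1 − p) and μ = −ln(1 − d), the risk with death competing is λ/(λ + μ) × (1 − e^−(λ+μ)). For p = 20%: 0.1902 (10% deaths) against 0.1951 (5% deaths), a risk ratio of 0.975. For p = 50%: 0.4774 against 0.4888, or 0.977. The size is the same as in the count model.

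**How many decedents would show no readmission.** Given death at a uniform time, the probability of no earlier readmission is (1 − e^−λ)/λ, where λ here is the decedent's readmission rate per 180 days. At λ = 0.6 it is 0.752; at λ = 1.8 it is 0.464. With 5% mortality (14 of 280), that is 10.5 or 6.5 deaths per arm.

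**What collecting deaths would give.** For 5% versus 10% with 280 per arm, the power to detect a mortality difference is Φ[(0.05 × √280 − 1.96 × √(2 × 0.075 × 0.925)) / √(0.05 × 0.95 + 0.10 × 0.90)] = Φ[(0.837 − 0.730)/0.371] = 0.61. The same formula gives 0.40 for 3% versus 6% and 0.98 for 5% versus 15%.

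**The case against.** The strongest reply is that the plan is silent rather than wrong, and that the numerical effect is slight. Much of this stands.

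- A reader might infer that everyone who dies is scored as readmission-free. The documents do not say so. Zero events is the default that follows from intent-to-treat and a readmissions-only audit. Anyone readmitted before death, or who dies during a captured readmission, still contributes an event; at k = 3, more than half of the 14 decedents would.
- A reader might infer that the model rules out time at risk. It does not. The listed terms are ones the model will include, covariates may be added, the link is left open, and an incidence rate ratio ordinarily implies a person-time denominator.
- A reader might infer that deaths could not be seen at all. Staff may meet them in the records or on the calls. What is missing is any commitment to record and report them.
- The exclusions for short life expectancy and for discharge to somewhere other than home, and the milder conditions that also qualify, lower expected mortality.
- A days-alive offset is not a neutral correction. At k = 3 it moves the ratio from 1.024 to 1.051, because events per day alive is a different estimand from events per randomised person.

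The omission itself survives all of this. Lower mortality is not zero mortality, and incidental knowledge of a death is no substitute for a date recorded in the same way in both arms.

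**Conclusion.** The point holds as a gap in data collection and reporting: follow-up audits are specified for readmissions only, and death has no planned place in the data or the results. A difference of 5% versus 10% in mortality would shift the primary IRR by about 2.5%, which is small beside the detectable ratios of roughly 0.48 to 0.75. These figures rest on assumed rates, evenly spread deaths and the stated multipliers.

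The tempting stronger reading is that harm would pass for benefit. The documents do not support it as a general claim: the direction reverses once decedents are readmitted at more than twice the survivors' rate, and nothing in the plan says which case applies. The main loss is interpretive, since a reduction in readmissions could not be set against deaths by arm. This is a cheap improvement, not a defect that overturns the design.

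**What to change.** **Mi Puente Protocol, record audit.** Add vital status and date of death to the items abstracted at 30 and 180 days. When a death is learned of at the month-3 or month-6 call, code it as death, with its date, and not as attrition.

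**SAP, Power and Sample Size and Analytic Plan.** State how a participant who dies enters the 30- and 180-day outcome, and whether the attrition allowance includes deaths. Report deaths by arm. Add a supportive analysis of readmission or death. Add a days-alive (person-time) analysis as a sensitivity analysis, leaving the primary model as it is.

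**Cost.** One or two extra fields in an audit already made for every subject, a disposition code on calls already planned, and two secondary analyses. The sample size, arms and visits do not change. Abstraction takes slightly longer, some out-of-hospital deaths may still be missed, and the mortality comparison would be descriptive unless the difference were large.
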